8.7. Composite Subject-level Response Analysis

As a supplementary analysis to the primary and key secondary endpoints for the study, and to support the interpretation of further clinical benefit, an analysis using a composite subject-level response will be performed based on a multi-domain responder index (MDRI). This MDRI will be defined to capture the totality of evidence using the 3 relevant clinical outcomes, 6MWD, FVC (% predicted), and MMT lower extremity score. The MDRI approach provides a framework for presenting the totality of data combining the 3 components which measure motor function, pulmonary function, and muscle strength, which are the domains that are impacted in individuals with LOPD. A clinically meaningful threshold for within-subject changes in each clinical outcome and the categorization of each outcome are provided in Table 8.

Table 8: Threshold for Defining Clinically Meaningful Within-subject Change

Clinical Outcome	Declining	Stable	Improving
6MWD ^a	< -6%	-6% to < +6%	\geq +6%
% predicted FVC ^b	< -3%	-3% to < +3%	\geq +3%
MMT lower extremity score ^a	< -7%	-7% to < +7%	\geq +7%

^a Threshold is based on the percentage change from baseline.

^b Threshold is based on the change from baseline.

The above thresholds are consistent with published MCID (minimal clinically important differences) values for comparable instruments in similar disease populations (Schrover, Evans et al. 2017; du Bois, Weycker et al. 2011; Baschung Pfister, de Bruin et al. 2018).

The ordinal composite response across all 3 ternary outcomes is defined as follows:

- 3 = significant improvement: subject is either improving on all 3 outcomes, or is improving on both 6MWD and % predicted FVC;
- 2 = moderate improvement: subject is improving on either 6MWD only, or % predicted FVC only, or both 6MWD and MMT lower extremity, or both % predicted FVC and MMT lower extremity;
- 1 = minor: subject is improving on MMT lower extremity score only;

- 0 = no improvement: subject is not improving on any of the 3 clinical outcomes.

The main interest for this analysis is the inter-group comparison. There is no intra-subject comparison for the MDRI approach.

This method defines a hierarchical ordinal categorical response variable, for which a continuation logit model (Agresti 2002) will be used to perform separate logistical regression analyses adjusting for baseline risk factors including ERT status (ERT-naïve or ERT-experienced), duration of prior alglucosidase alfa (only for ERT-experienced subjects), gender, and baseline age.

The results of these separate logistic regression analyses are then pooled to test the overall null hypothesis that treatment with ATB200/AT2221 is less effective than alglucosidase alfa/placebo with respect to either the positive composite response (ie, significant improvement) or the negative response (ie, minor/no improvement). The inter-group comparison will be based on the combined analysis of comparisons of the positive response rates of significant improvements and the negative response rates of minor/no improvement.

Additional details regarding the separate logistic regression analyses and test against the overall null hypothesis are described below.

The “significant improvement” response category is considered as positive response, the “moderate improvement” category is considered as stable response, and “minor/no improvement” is considered as negative response. Treatment (ie ATB200/AT2221) is expected to have high positive responses and low negative responses, while the control (ie, alglucosidase alfa/placebo) is expected to have high negative responses and low positive responses). Separate logistic regression models are used to analyze and test (1) positive responses vs. not positive responses (where “not positive responses” includes the “moderate improvement” and “minor/no improvement” categories; (2) negative responses vs. stable responses, conditional on subjects who are not positive responders.

The respective hypotheses for Test 1 and Test 2 are stated as follows: $H_{10}: \delta_1 \leq 0$ vs. $H_{1A}: \delta_1 > 0$ and $H_{20}: \delta_2 \leq 0$ vs. $H_{2A}: \delta_2 > 0$, where δ_1 and δ_2 are the effect sizes for comparing treatment to control for Test 1 and Test 2 respectively.

Let the logistic regression model for Test 1 be:

$$\text{logit}(p_{1,Positive}) = \ln \frac{p_{1,Positive}}{p_{1,Not pos}} = \beta_{1,0} + \beta_{1,1} \text{TRT} + \beta_{1,2} \text{ERT} + \beta_{1,3} \text{DUR} + \beta_{1,4} \text{SEX} + \beta_{1,5} \text{AGE}$$

and Test 2 be:

$$\text{logit}(p_{2,Negative}) = \ln \frac{p_{2,Neg}}{p_{2,Stable}} = \beta_{2,0} + \beta_{2,1} \text{TRT} + \beta_{2,2} \text{ERT} + \beta_{2,3} \text{DUR} + \beta_{2,4} \text{SEX} + \beta_{2,5} \text{AGE}$$

For any coefficient β , the Wald statistic is given by $Wald = b/se_b$, where b is the estimate for β and se_b is the standard error for β , and the Wald statistic is approximately normally distributed. Therefore, in testing the null hypothesis about the treatment effect, say $\beta_{1,2} = 0$ (for Test 1), the test statistic for treatment effect is: $(b_{1,2} - 0)/se_b = b_{1,2}/se_b$.

Let $Z_1 = b_1/se_{b_1}$ and $Z_{2/1} = b_{2/1}/se_{b_{2/1}}$ be the test statistics for testing treatment effect in Test 1 and Test 2 respectively, where Z_1 and $Z_{2/1}$ are standardized to have standard normal distributions (so that each has mean = 0 and variance = 1).

The inter-group comparison is based on the combined analysis of the positive response rates of significant improvements and the negative response rates of minor/no improvement. The overall null and alternative hypothesis ($H_0: H_{10} \cap H_{20}$) is tested against the alternative hypothesis ($H_A: H_{1A} \cup H_{2A}$) based on the combination test statistic:

$$Z = \frac{w_1}{w_1+w_2} Z_1 + \frac{w_2}{w_1+w_2} Z_{2/1}, \text{ where } w_1 \text{ and } w_2 \text{ are weights (constants) for the random}$$

variables Z_1 and $Z_{2/1}$ respectively (Rpatel 2019). The weights, w_i , represent the information fraction in test i . The expected value of Z is given by:

$$E(Z) = \frac{w_1}{w_1+w_2} E(Z_1) + \frac{w_2}{w_1+w_2} E(Z_{2/1}) = 0, \text{ under } H_0.$$

Assuming independence of Z_1 and $Z_{2/1}$, the variance of Z is given as:

$$\begin{aligned} Var(Z) &= \left(\frac{w_1}{w_1+w_2}\right)^2 Var(Z_1) + \left(\frac{w_2}{w_1+w_2}\right)^2 Var(Z_{2/1}) \\ &= \left(\frac{w_1}{w_1+w_2}\right)^2 + \left(\frac{w_2}{w_1+w_2}\right)^2 \end{aligned}$$

Inference is based on the standardized score Z_w , where

$$Z_w = \frac{\frac{w_1}{w_1+w_2} Z_1 + \frac{w_2}{w_1+w_2} Z_{2/1}}{\left[\left(\frac{w_1}{w_1+w_2}\right)^2 + \left(\frac{w_2}{w_1+w_2}\right)^2\right]^{1/2}}$$

follows the standard normal distribution under the null hypothesis. A 1-sided p-value for testing against the overall null hypothesis H_0 is given by $p = 1 - \Phi(z_w)$, where $\Phi(\cdot)$ is the cumulative distribution function of a random variable that follows the standard normal distribution.

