8.8.5. Proportion Improving on Both 6MWD and % Predicted FVC

The proportion of subjects improving on both 6MWD and % predicted FVC (where definition of improvement is provided in Section 8.7) will be compared between the 2 treatment groups using a logistic regression model adjusting for baseline age, ERT status, gender, baseline height, and baseline weight. The number and percent of subjects improving will be presented for each treatment group, and the p-value for comparing between the 2 treatment groups and the 95% confidence interval for the treatment difference will be calculated from the logistic regression model.

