  lsmeans TRTPN / OM s alpha=0.05 cl diff; ** Obtain lsmeans and lsmean  
differences;  
  
  lsmestimate TRTPN "Treat vs. Control at Week 52" 1 -1 / upper  
  testvalue=0; **Get treatment diff and 1-sided p-value at W52 *;  
  
  lsmestimate TRTPN `Treat vs. Control at Week 52' 1 -1 / testvalue=0  
  alpha=0.05 cl; **Get treatment diff, 2-sided p-value, 95% CIs at W52*;
```

Sample Code for the Analysis of Composite Endpoint

```
*****  
* Implement separate logistic analyses for positive responses and *  
* negative responses, and then combine the two results using weights. *  
*  
* Assume input dataset (COMPOS) is structured as below, and has the *  
* following variables: RESPONSE, TRTPN, ERTSTA, DUR, SEX, AGEBL *  
*  
  1 1 N 2.4 F 0  
  3 1 N 3.5 M 0  
  1 1 E 2.7 M 37  
  0 2 N 5.6 F 0  
  3 1 E 7.0 M 67  
  3 2 N 2.0 F 0  
  2 1 E 4.1 M 64  
  1 2 N 4.8 M 0  
  0 2 E 7.7 F 28  
  3 1 E 5.5 F 32  
  2 2 E 6.3 F 48  
  . . . . .  
  
* RESPONSE variable = composite response with values 0, 1, 2, 3 *  
* TRTPN = Treatment group (1 = new treatment, 2 = control) *  
* ERTSTA = ERT status (Experienced or Naïve) *  
* DUR = duration of ERT: value for ERT-experienced, and 0 for naïve.*  
*****;  
  
** Analysis of positive responses vs. not positive responses **;
```

```
data comp1;
  set compos;
  if response=3 then resp1='Y';
  else resp1='N';
run;

** Analysis of stable responses vs. negative responses;
data comp2;
  set compos;
  if response=3 then delete;
  if response=2 then resp2='Y';
  else resp2='N';
run;

** Run two separate logistic regression models **;
ods output ParameterEstimates=test1;
proc genmod data=comp1;
  class TRTPN ERTSTA SEX;
  model resp1(event='Y') = TRTPN ERTSTA DUR SEX AGEBL / dist=binomial
                        link=logit type3;
run;

ods output ParameterEstimates=test2;
proc genmod data=comp2;
  class trt ert;
  model resp2(event='Y') = TRTPN ERTSTA DUR SEX AGEBL / dist=binomial
                        link=logit type3;
run;

data combo;
  merge test1(where=(level1='1') keep=level1 estimate stderr
              rename=(estimate=estimate1 stderr=stderr1))
        test2(where=(level1='1') keep=level1 estimate stderr
              rename=(estimate=estimate2 stderr=stderr2));
run;

** Calculate the weights, combine the test statistics and obtain the **;
** p-value using weight as the inverse of the standard error estimate **;
data combo2;
  set combo;
  w1=1/stderr1**2;
  w2=1/stderr2**2;
  z1=estimate1/stderr1;

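### The planned two-step test of the composite index (MDRI) does not use the muscle strength result, although SAP 8.7 presents the index as combining three domains

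*SAP*

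**What the plan says.** SAP 8.7 sets up the MDRI as a supplementary analysis meant to give the overall picture across three outcomes, "combining the 3 components which measure motor function, pulmonary function, and muscle strength". Table 8 classes each outcome as declining, stable or improving. The score is then defined as follows:

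- Score 3: "3 = significant improvement: subject is either improving on all 3 outcomes, or is improving on both 6MWD and % predicted FVC".
- Score 2: "2 = moderate improvement: subject is improving on either 6MWD only, or % predicted FVC only, or both 6MWD and MMT lower extremity". A subject whose FVC and MMT improve without 6MWD is placed here too.
- Score 1: "1 = minor: subject is improving on MMT lower extremity score only".
- Score 0: none of the three outcomes improving.

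For the analysis, score 3 is the positive response and score 2 the stable response. The combined minor/no-improvement group (scores 1 and 0) "is considered as negative response". Test 1 compares score 3 with the rest. Test 2 compares the stable with the negative response among subjects who are not positive. The two Wald statistics are combined into one weighted Z with a one-sided p-value. The Appendix 3 code matches: after deleting score 3, the second data step reads "if response=2 then resp2='Y", and every other score becomes N.

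The pooled level comes from protocol 15.3.2.3.1, which names three levels, the lowest being minor/no improvement. The protocol leaves the improvement criteria to the SAP.

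SAP 8.8.5 separately compares "The proportion of subjects improving on both 6MWD and % predicted FVC" between arms, taking its definition of improvement from 8.7.

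**The concern.** A reader told that an index combines walking, breathing and strength will take a favourable p-value as evidence touching all three. If one domain cannot move a subject between the groups being compared, the p-value says nothing about it, in either direction. Strength gains confined to one arm would not help the index, and strength losses confined to one arm would not hurt it.

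There is also a risk of double counting. If Test 1 uses the same response event as 8.8.5, two favourable results could be read as separate support when they rest on one event.

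**Working it through.** The SAP gives no power or sample size for the MDRI, so there is no figure of its own to reproduce. The check is an enumeration of the definitions.

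**Inputs.** The three states per outcome from SAP Table 8; the score definitions in 8.7; the pooling in 8.7; the coding in Appendix 3.

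**Step 1. List the profiles.** Three outcomes with three states give 3 × 3 × 3 = 27 profiles, or 9 combinations of 6MWD and FVC status with three MMT states in each.

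**Step 2. Score them.** Only improving counts towards the score.

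| Improving on | Combinations (of 9) | Score, MMT not improving | Score, MMT improving | Analysed category |
|---|---|---|---|---|
| Both 6MWD and FVC | 1 | 3 | 3 | Positive |
| Exactly one of them | 4 | 2 | 2 | Stable |
| Neither | 4 | 0 | 1 | Negative |

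Profiles by analysed category: positive 1 × 3 = 3, stable 4 × 3 = 12, negative 4 × 3 = 12. The 12 negative profiles split into 4 × 2 = 8 with score 0 and 4 × 1 = 4 with score 1. Total 3 + 12 + 12 = 27.

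**Step 3. Let MMT vary within each 6MWD-by-FVC combination.**

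- The 0–3 score changes in 4 of 9 combinations, always between 0 and 1.
- The analysed category changes in 0 of 9.
- The two response variables in the Appendix 3 code change in 0 of 9.

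In all 27 profiles the analysed category equals the number of improvements among 6MWD and FVC: 2 is positive, 1 is stable, 0 is negative. MMT decline has no effect either: a subject improving on 6MWD and FVC while declining on MMT still scores 3.

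**Step 4. Carry this to the test.** The SAP's standardised statistic simplifies to

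Zw = (w1·Z1 + w2·Z2|1) / √(w1² + w2²),

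with w = 1/SE² in the sample code. Each Z and w depends only on the two response variables and the covariates. For a fixed set of analysed subjects, none can change with MMT.

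As an illustration, one data set was simulated with 66 and 33 subjects. The improvement rates were assumed: 6MWD 45% versus 30%, FVC 35% versus 20%. MMT was then set four ways:

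| MMT improving in | Score 0 | Score 1 | Score 2 | Score 3 | Zw |
|---|---|---|---|---|---|
| Nobody | 47 | 0 | 44 | 8 | 1.857 |
| Everybody | 0 | 47 | 44 | 8 | 1.857 |
| ATB200/AT2221 arm only | 20 | 27 | 44 | 8 | 1.857 |
| Control arm only | 27 | 20 | 44 | 8 | 1.857 |

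The runs gave convergence warnings from the logistic fits, so the value 1.857 carries no meaning. What matters is that the fits receive identical inputs in all four rows.

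**Step 5. Compare with 8.8.5.** Score 3 holds exactly when 6MWD and FVC both improve, whatever the MMT. That is the 8.8.5 event. The covariates differ: 8.7 adjusts for ERT status, duration of prior alglucosidase alfa, gender and age; 8.8.5 for age, ERT status, gender, height and weight.

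**Step 6. Effect of testing 1 versus 0.** If scores 1 and 0 were kept apart in the analysis, MMT would change the analysed category in 4 of 9 combinations, those where neither 6MWD nor FVC improves.

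**The case against.** The strongest defence has three parts. First, ranking MMT below 6MWD and FVC is a deliberate and legitimate hierarchy, and the pooled lowest level was set in the protocol. Secondly, the MDRI is supplementary and outside the testing hierarchy. Thirdly, strength is examined directly elsewhere: lower-extremity MMT is the second key secondary endpoint (SAP 8.3.2, 8.4), with ANCOVA and a supportive MMRM (8.6), and 8.8.2 adds tabulated MMT changes and further MMT and QMT endpoints.

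The second and third parts stand, and they limit the consequence. The first stands only in part. A lower-ranked component would normally break ties. The score does give MMT that role (1 versus 0), and the pooling then removes it from the test. The protocol fixed the pooled level but left the criteria to the SAP, and the SAP's criteria place MMT's only contribution inside that level.

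A reader might infer more than the documents support:

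- *That MMT plays no part in the MDRI at all.* It separates 1 from 0 in the defined score and would show in a four-level tabulation. Only the planned test ignores it.
- *That muscle strength is lost from the trial's evidence.* It is not, given the key secondary endpoint.
- *That Test 1 and 8.8.5 are the same analysis apart from covariates.* The response event is the same, but neither section states an analysis population or a rule for a missing component. If a missing MMT made the composite missing, the subjects analysed could differ.
- *That a particular amount of power is forgone.* Any such figure depends on improvement rates and correlations between domains that the documents do not give, so none is offered here.

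**Conclusion.** The point holds, in this limited form. The planned MDRI test is a test of the number of improvements on 6MWD and FVC. MMT changes the analysed category in 0 of 9 combinations, and the p-value is the same whatever the MMT data are. The description in 8.7 therefore attributes to the analysis a property that it lacks. The positive response is the 8.8.5 event, so agreement between the two is not independent support.

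The result follows from the definitions and needs no assumption about effect sizes. Its one condition is that the set of analysed subjects is fixed: a missing MMT could affect who is included, on which 8.7 is silent, but not the category of anyone included. No confirmatory conclusion is affected. The defect lies in the description and coding of a supplementary analysis, but it is worth correcting because the index exists to support interpretation across the three domains.

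**What to change.** Choose one of two routes before the SAP is final.

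1. **Let MMT enter the test.** Keep the four-level score and its priority for 6MWD and FVC. Add a third continuation logit for score 1 versus score 0 among subjects scoring 0 or 1, with the same covariates and improvement coded as the event. Extend the hypotheses in 8.7 and the Appendix 3 code to three terms: Zw = (w1·Z1 + w2·Z2 + w3·Z3) / √(w1² + w2² + w3²).
2. **Keep the two-step test and describe it accurately.** State in 8.7 that the tested result is a 6MWD/FVC index that does not reflect muscle strength. Tabulate all four score levels by arm. State that Test 1 uses the same response event as 8.8.5 and is not independent support.

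Route 2 needs only wording and one table. Route 1 is a small rewrite of a supplementary analysis and departs from the protocol's pooled minor/no-improvement level; SAP Section 2 allows this, since the final SAP takes precedence over the protocol on analysis methods. Neither route needs new data. Replacing the score with a simple count of improved domains, or splitting score 2 by MMT, would also bring MMT in. The count would abandon the pre-specified ordering and the split would rework it, so neither is needed to repair this defect.

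### The supplementary composite (MDRI) defines a declining class for each domain but scores only improvement, so worsening in 6MWD or FVC can sit inside moderate improvement and preventing decline earns nothing within the index

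*SAP*

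**What the plan says.** SAP Section 8.7 introduces the MDRI "As a supplementary analysis to the primary and key secondary endpoints for the study" and gives its aim: "This MDRI will be defined to capture the totality of evidence using the 3 relevant clinical outcomes". Table 8 sets cut-offs for three classes per domain:

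- 6MWD: declining below -6%, improving at +6% or more (percentage change from baseline).
- % predicted FVC: declining below -3, improving at +3 or more (change from baseline).
- MMT lower extremity: declining below -7%, improving at +7% or more (percentage change from baseline).

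The score is then introduced with "The ordinal composite response across all 3 ternary outcomes is defined as follows". A score of 3 goes to anyone with 6MWD and FVC both in the improving class, whatever MMT does. The next rule down begins "2 = moderate improvement: subject is improving on either 6MWD only, or % predicted FVC only, or both 6MWD and MMT lower extremity", and it treats FVC paired with MMT in the same way. A score of 1 is for those whose sole gain is in MMT. At the bottom of the scale the wording is "0 = no improvement: subject is not improving on any of the 3 clinical outcomes".

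For the two logistic models, score 3 is the positive response, scores 0 and 1 are the negative response, and the score 2 "category is considered as stable response". The sample code in SAP Appendix 3 starts from a ready-made 0 to 3 response and holds no decline variable. Protocol Section 15.3.2.3.1 names three improvement levels for the composite and leaves the criteria to the SAP.

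**The concern.** The score is described as built on three-class outcomes but treats each domain as improving or not. Table 8's declining column enters no score, neither logistic model and no line of the sample code.

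Two things follow. First, worsening that the SAP itself calls clinically meaningful can be reported under an improvement label. Second, holding a patient stable is worth no more than letting that patient decline, and both count as a negative response. The labels add to the confusion: score 2 is an improvement level in the definition and the stable response in the model, while a subject who really is stable on all three domains is negative.

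This matters because the index is offered as totality evidence of benefit in a progressive disease. Protocol Section 6.1 describes a plateau and then decline on alglucosidase alfa, and the matched control slopes in SAP Appendix 1 are negative (-2.15% and -0.65% predicted 6MWD). Less decline is therefore one form that benefit over the comparator could take.

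**Working it through.** **The plan's own figure.** The documents give no power or response rate for the MDRI. The only design figure is for the primary endpoint: 66 + 33 subjects and standardized effect 0.7 give about 90% power. It reproduces: noncentral t with 97 df gives 0.902, and 99/(1 - 0.10) = 110. It does not bear on this point.

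**Step 1: enumerate the rules (no assumptions needed).** Three classes in three domains give 3 x 3 x 3 = 27 patterns.

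- Score 3: 6MWD and FVC both improving, MMT any class: 1 x 1 x 3 = 3 patterns. One has MMT declining.
- Score 2: exactly one of 6MWD and FVC improving: 2 (which one) x 2 (other stable or declining) x 3 (MMT) = 12. The other is declining in 2 x 1 x 3 = 6. No domain declines in 2 x 1 x 2 = 4, so 12 - 4 = 8 have some domain declining.
- Score 1: neither 6MWD nor FVC improving, MMT improving: 2 x 2 x 1 = 4.
- Score 0: nothing improving: 2 x 2 x 2 = 8, from all stable to all declining.

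The total is 3 + 12 + 4 + 8 = 27. Each domain is declining in 9 patterns, so there are 27 declining entries. Changing each to stable and rescoring alters the score in 0 of 27.

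Of the 9 patterns with FVC declining, 3 score 2 (6MWD improving), 2 score 1 and 4 score 0. The counts for 6MWD declining are the same.

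**Step 2: could it happen often? (illustration).** Inputs are ATB200-02 Cohort 1, Month 12, from Protocol Tables 2 and 3: baseline 6MWD 397.2 m; change +42.2 m (SD 46.5, n = 10); FVC change -3.3 (SD 6.1, n = 9). Normality is assumed and the 6% cut-off is applied to the mean baseline: 0.06 x 397.2 = 23.8 m.

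- P(6MWD improving) = 1 - Φ((23.8 - 42.2)/46.5) = 0.65
- P(FVC declining) = Φ((-3 + 3.3)/6.1) = 0.52
- P(FVC improving) = 1 - Φ((3 + 3.3)/6.1) = 0.15
- P(6MWD declining) = Φ((-23.8 - 42.2)/46.5) = 0.08

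If the domains are independent, P(score 2) = 0.654 x 0.849 + 0.346 x 0.151 = 0.61. The part with 6MWD or FVC declining is 0.654 x 0.520 + 0.078 x 0.151 = 0.35. The share is 0.35/0.61 = 58%. With correlation 0.5 it is 50%. Cohort 3 (n = 5) gives about 40%.

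**Step 3: compare the index with a net score.** The net score adds +1, 0 or -1 per domain from Table 8. Simulated trials have 73 vs 37 subjects (110 at 2:1) and one-sided alpha 0.025. The MDRI test is the Appendix 3 combination without covariates; the net score uses a rank test.

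| Scenario (assumed) | MDRI | Net score |
|---|---|---|
| 0.5 SD shift in every domain | 48% | 88% |
| Improving 40% vs 20%, declining 25% in both arms | 72% | 63% |
| Declining 17.5% vs 35%, improving 20% in both arms | 2% | 60% |

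The shift scenario uses control means of -2%, -3.3 points and -2%, SDs of 11.7% (46.5/397.2), 6.1 and 12%, and correlation 0.3. The control means, the MMT SD and the correlation are assumptions. Domains are independent in the other two rows, and their rates are assumptions. In the last row the MDRI's null is true by construction, so 2% only confirms that the index does not respond to decline.

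**The case against.** The best defence is that scoring improvement only is a legitimate, pre-specified choice. The protocol's composite has improvement levels only, the SAP calls it a responder index, and the expected treatment effect is gain: the Appendix 1 slopes on ATB200/AT2221 are +5.87% and +12.61% predicted 6MWD, against small control declines. If benefit comes only as more improvement, the present index is the more powerful one (72% vs 63%). This stands as a reason to keep the index. It does not explain why Table 8 defines a class that nothing uses, or why the score is said to rest on ternary outcomes.

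Decline is also visible elsewhere: the continuous MMRM and ANCOVA comparisons, the 12-month slopes for 6MWD and FVC (8.5.1.1), the tabulated MMT changes (8.8.2), the FVC non-inferiority check (8.6) and the declining category of the SGIC. This stands too, and it limits the point to the MDRI.

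One might read the word only in score 2 as requiring that the other domains do not decline. That does not help: a subject with 6MWD improving and FVC declining would then fit no level, because score 0 requires improvement on none.

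A net score has its own flaw. One gain and one loss cancel to 0, the same as all stable, and MMT gets equal weight with 6MWD and FVC. That is a reason to report it beside the index, with a cross-tabulation.

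**Conclusion.** The point holds for the MDRI, as a matter of definition. The 0-of-27 result needs no assumption about data. Stable on all and declining on all are both negative responses, and half of the score 2 patterns (6 of 12) contain a declining 6MWD or FVC.

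A reader might infer more than the documents support:

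- That any subject who declines on FVC or 6MWD is called moderately improved. This happens only if the other of the two improves: 3 of 9 patterns. The rest score 0 or 1.
- That the trial's conclusions are at risk. The MDRI is supplementary and outside the testing order in SAP Section 8.4, so no primary or key secondary result changes.
- That 50% to 58% of moderate responders in this trial will have a declining domain. That range rests on 10 and 9 subjects from an open-label study, with normality and correlation assumed. It shows the pattern is plausible; it is not a forecast.
- That a net score is always better. It gains under a uniform shift and loses when only improvement differs.

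The consequence is moderate: an index presented as totality evidence can show worsening as improvement and cannot register prevented decline.

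**What to change.** Before database lock, add to SAP Section 8.7:

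1. A pre-specified analysis that scores each domain +1, 0 or -1 from the existing Table 8 classes, sums the three, and compares the arms with a rank or proportional-odds test stratified by ERT status. Report it beside the 0 to 3 index.
2. A table of declining, stable and improving for each domain, by arm and by MDRI level, so that subjects scored 2 or 3 with a declining domain can be seen. This is needed because gains and losses cancel in a net score.

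If the sponsor would rather keep the present levels and bar scores 2 and 3 to anyone with a declining domain, the rule must give every one of the 27 patterns a level. A simple bar leaves 6MWD improving with FVC declining without one: score 1 requires improvement on MMT alone, and score 0 requires none.

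The cost is SAP text and programming, with no new data. The trade-off is the lower power of the net score if benefit appears only as more improvement with decline unchanged, which is why the existing index should stay alongside it.

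### SAP 8.7 prints the second test of the composite (MDRI) analysis in the opposite direction to its own hypotheses and to Appendix 3, so benefit on one part cancels benefit on the other

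*SAP*

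**What the plan says.** SAP Section 8.7 classes significant improvement as a positive response, moderate improvement as stable, and minor or no improvement as negative. It gives the expected direction: "Treatment (ie ATB200/AT2221) is expected to have high positive responses and low negative responses". The overall null is that "treatment with ATB200/AT2221 is less effective than alglucosidase alfa/placebo with respect to either the positive composite response" or the negative one, and the alternatives are delta1 > 0 and delta2 > 0.

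Test 1 is positive versus not positive, with model `ln(p_Positive / p_NotPositive)`. Test 2 is "2) negative responses vs. stable responses, conditional on subjects who are not positive responders", with model `ln(p_Neg / p_Stable)`. The section defines Z1 and Z2/1, each as coefficient over standard error, to "be the test statistics for testing treatment effect in Test 1 and Test 2 respectively". It adds them with positive weights and standardises the sum to Z_w. "A 1-sided p-value for testing against the overall null hypothesis" is then 1 − Φ(z_w). No step changes the sign of Z2/1.

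Appendix 3 heads the same step "Analysis of stable responses vs. negative responses". It codes the event with "if response=2 then resp2='Y" and so on, where response 2 is moderate improvement (stable). It models that event, keeps the treatment estimate for level 1 (the new treatment), and takes the same upper-tail p-value.

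**The concern.** In the formulas of 8.7, benefit raises the Test 1 coefficient and lowers the Test 2 coefficient. Adding the two Z values without reversing the second sets the benefits against each other and counts an excess of negative responses as evidence for the drug. A programmer working from 8.7 and one working from Appendix 3 would run different tests on the same data and could reach opposite conclusions. SAP Section 2 ranks the SAP above the protocol, but no rule ranks the text of 8.7 against code that Appendix 3 calls sample code. The MDRI is the analysis meant to draw together 6MWD, % predicted FVC and lower-extremity MMT.

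**Working it through.** **Plan's own figures.** The SAP gives no power or response rates for the composite. The trial sizing in SAP 4.3 does reproduce: 66 vs 33 and standardised effect 0.7 give noncentrality 0.7 × √(66×33/99) = 0.7 × √22 = 3.28. With 97 df at one-sided 0.025, power is 0.902, and 99/0.9 = 110 randomised. Those arm sizes are used below.

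**Direction, with illustrative counts** (positive/stable/negative): new drug 20/26/20 of 66, control 4/11/18 of 33. The drug is better on both parts.

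- Test 1: log OR = ln[(20×29)/(46×4)] = 1.148; SE = √(1/20 + 1/46 + 1/4 + 1/29) = 0.597; Z1 = 1.92.
- Test 2, stable as event (Appendix 3): log OR = ln[(26×18)/(20×11)] = 0.755; SE = √(1/26 + 1/20 + 1/11 + 1/18) = 0.485; Z2 = +1.56.
- Test 2, negative as event (8.7): log OR = −0.755, same SE, Z2 = −1.56.
- Weights w = 1/SE²: w1 = 2.81, w2 = 4.26. Z_w = (w1·Z1 + w2·Z2)/√(w1² + w2²).
- Appendix 3 direction: Z_w = 2.36, p = 0.009. As printed in 8.7: Z_w = −0.24, p = 0.60.

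**Rejection rates.** All response rates are assumed. Each scenario used 200,000 simulated trials of 66 vs 33, unadjusted log odds ratios, w = 1/SE², and rejection at Z_w > 1.96. Ranges cover adding 0.5 to cells only when one is zero, or always. The third column is the stable share among non-positive responders, which is what Test 2 compares (for example 40/(40+35) = 53% against 35/(35+55) = 39%).

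| Drug vs control, positive/stable/negative % | Benefit falls on | Stable share of non-positives | Appendix 3 direction | 8.7 as printed |
|---|---|---|---|---|
| 25/40/35 vs 10/35/55 | both | 53% vs 39% | 41% | 0.5% |
| 30/40/30 vs 10/30/60 | both | 57% vs 33% | 77% | 0.1% |
| 18/40/42 vs 12/36/52 | both, small | 49% vs 41% | 11–12% | 0.7% |
| 40/33/27 vs 15/40/45 | mainly Test 1 | 55% vs 47% | 46% | 11% |
| 40/32/28 vs 15/42.5/42.5 | mainly Test 1 | 53% vs 50% | 34% | 19% |
| 40/30/30 vs 15/42.5/42.5 | Test 1 only | 50% vs 50% | 26% | 25–26% |
| 15/50/35 vs 15/40/45 | Test 2 only | 59% vs 47% | 11–12% | 0.1% |

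**Harm on Test 2 only** (control 15/45/40, positives unchanged). As printed, 8.7 gives p < 0.025 in 4.5–5.0%, 11–12%, 21–23% and 37–39% of runs for a rise in negative responses of 5, 10, 15 and 20 points. The Appendix 3 direction gives 0.5% or less.

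**No effect** (three common response profiles): 1.4–1.9% in the Appendix 3 direction, 1.6–2.1% as printed.

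**Covariates.** The check was repeated with ERT status, duration, sex and age in both models: 8,000 runs per scenario, 30 of 99 naïve, covariates assumed non-prognostic, and 33–267 non-converged runs dropped. The first two rows give 41.6% vs 0.7% and 77.9% vs 0.2%. The two mainly-Test-1 rows give 49.7% vs 12.7% and 36.1% vs 21.3%. Harm of 5, 10 and 20 points gives 5.5%, 12.2% and 39.1% as printed.

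**Weights.** With w = 1/SE instead of 1/SE², the first row becomes 46–47% vs 0.9%, so the weight definition matters far less than the direction.

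**The case against.** The intended test can be inferred. The null, the expected direction and delta2 > 0 all point to benefit, and Appendix 3 supplies code that is correctly oriented. Only the Test 2 label and formula in 8.7 are reversed. Section 8.7 also never equates delta2 with the Test 2 treatment coefficient, so a benefit-oriented delta2 is a possible reading. Harm follows only if someone codes the printed formula and does not notice that fewer negative responses lower Z_w.

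The intention is indeed clear, and that settles which way to correct. It does not rescue the printed procedure: if delta2 is benefit-oriented, Z2/1 needs a reversal that 8.7 does not give. The appendix cannot simply be taken as the reference, because it is labelled sample code and has slips of its own.

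The limits on the figures stand. Section 8.7 sets no significance threshold for the MDRI and names no analysis set, so one-sided 0.025 and 66 vs 33 are borrowed for illustration. The loss depends on how benefit splits between the two tests, and the harm scenarios are hypothetical. It is also true that the MDRI is supplementary, that 6MWD, FVC and MMT have their own analyses, and that joint 6MWD/FVC improvement is tested in SAP 8.8.5.

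**Conclusion.** The concern holds. Test 2 as printed in 8.7 runs against the section's own hypotheses and against Appendix 3. The reversal follows from the formulas and needs no assumption; its size does. Under the assumed rates, the printed form loses nothing when benefit is confined to Test 1. It loses part of the power when benefit is mainly there, and nearly all of it when benefit is substantial on both parts or confined to Test 2. It also rewards an increase in negative responses: slightly for a 5-point rise, and in over a third of trials for a 20-point rise. Type I error under no effect is not inflated, and the gatekept primary and key secondary tests in SAP 8.4 are untouched. The correction should be made, but it does not threaten the trial's main conclusions.

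**What to change.** In SAP 8.7, describe Test 2 as stable versus negative among subjects who are not positive responders, and print the model as `ln(p_Stable / p_Neg)`. Alternatively, keep the printed model and enter −Z2/1 in the combination. Either way, state that delta2 > 0 means benefit, so that 8.7 and Appendix 3 specify one test.

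Three smaller slips can be cleared in the same edit:

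- The sentence beginning "Therefore, in testing the null hypothesis about the treatment effect, say" goes on to name beta(1,2), which multiplies ERT status. The treatment coefficients are beta(1,1) and beta(2,1).
- The CLASS line of the second GENMOD step in Appendix 3 names variables that are not in the listed dataset. It should read TRTPN ERTSTA SEX, as in the first step.
- The code comment describes the weight as inverse standard error, while the code uses inverse variance (1/SE²). Correct the comment.

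The cost is one formula and a few words in 8.7, plus one CLASS line and one comment in Appendix 3. No new data are needed. The change should be made before unblinding, so that nobody has to choose between two tests with the results in hand.
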